### 11.3 Clinical Laboratory Evaluations

The laboratory tests for hematology, biochemistry, and coagulation listed in the Schedule of Assessments of the protocol will be summarized (in the same sequence as in the protocol). Separate summary tables for hematology, biochemistry, and coagulation will be provided. Descriptive statistics as specified in Section 7 will be presented by treatment and total at scheduled visits for observed values and change from baseline. Number and percentage of

subjects will be presented for categorical tests by treatment and total at scheduled visits. The names and units of the laboratory tests will be used as provided in the data.

The following laboratory tests feeding into the SOFA score (see Section 10.2.1) will be indicated in the laboratory summary tables as SOFA score components: platelet count, bilirubin, creatinine. These tests will also be flagged in the listings as components of the SOFA score.

Laboratory values outside the normal range will be graded following Common Terminology Criteria for Adverse Events (CTCAE) 5.0 by clinical review. For laboratory tests with values outside normal range, the number and percentage of subjects in each grade will be presented.

For the definition of the baseline assessment see Section 8.2.3.

The denominator in percentage calculation at each scheduled visit will be based on the number of subjects with a non-missing value at each visit.

By-subject listings will be provided based on the ITT Analysis Set (date [and time] of sampling, test result, normal range, comments if applicable will be presented in a separate listing):

- Laboratory data for subjects with values outside the normal range;
- Hematology tests including flags for values outside the normal range and change from baseline;
- Biochemistry tests including flags for values outside the normal range and change from baseline;
- Coagulation tests including flags for values outside the normal range and change from baseline;
- Urinalysis tests.

## 11.4 Other Safety Measures

### 11.4.1 Vital Signs

Vital signs (blood pressure [systolic, diastolic], heart rate, respiratory rate) will be summarized by treatment and total at scheduled visits and time points. Descriptive statistics as specified in Section 7 will be presented for observed values and change from baseline.

For the definition of the baseline assessment see Section 8.2.3.

A by-subject listing will be provided based on the ITT Analysis Set (date [and time] of assessment, subject's position, location of body temperature measurement, test [blood pressure: systolic and diastolic; heart rate, respiratory rate, temperature, height and body weight at Screening], test result, change from baseline). Another by-subject listing will be provided for the hypotension assessment feeding into the SOFA score.

#### 11.4.2 Respiratory Tests

Respiratory tests as entered in the Respiratory Parameter CRF (respiratory rate, peripheral oxygen saturation [SpO2], FiO2, PaO2) will be summarized by treatment and total at scheduled visits and time points. Descriptive statistics as specified in Section 7 by treatment group will be presented for observed values and change from baseline. The respiratory component of the SOFA score, PaO2/ FiO2, will be analyzed in the same way as the other respiratory tests.

For the definition of the baseline assessment see Section 8.2.3.

A by-subject listing will be provided based on the ITT Analysis Set (date [and time] of assessment, test [respiratory rate, SpO2, FiO2, PaO2, PaO2/FiO2], test result, change from baseline). PaO2/FiO2 will be flagged in the listing as a component of the SOFA score.

#### 11.4.3 Glasgow Coma Scale (SOFA Score Component)

Number and percentages of subjects in the response categories of the 3 features (eye opening, best verbal response, and best motor response) and descriptive statistics as specified in Section 7 for the total score will be presented by treatment group at scheduled visits.

A by-subject listing will be provided based on the ITT Analysis Set (date and time of the assessment, feature, scale response, score).

#### 11.4.4 Physical Examination

Date and assessment performed for physical examination will be listed based on the ITT Analysis Set.

## 12 Pharmacokinetic Analyses

The PK analysis will be performed using the PK Analysis Set.

PPD will conduct the derivation of the PK parameters under the supervision of the CSL Behring Clinical Pharmacology department. All noncompartmental analyses will be

performed according to [PK-GDL-01](#). PK parameters will be derived based on the CSL312 concentration after the administration of CSL312 on Day 1.

After data base lock, CSL will produce all SDTM domains needed for the PK analysis. The PC domain containing the CSL312 concentrations, nominal blood sampling times, actual sampling time relative to the start of the dose infusion, actual dosing and infusion durations and the PP domain containing the PK parameters will be provided. Any CSL312 plasma concentrations which will have been excluded from the derivation of the PK parameters will be flagged in the data.

**PPD** will produce the TFLs for the CSL312 plasma concentrations and the PK parameters as specified below.

### 12.1 Drug Concentration Measures

The handling and imputation of below limit of quantification (BLQ) values for PK parameter derivation is described in [PK-GDL-01](#). The imputation rules below will be used for summary statistics of CSL312 plasma concentrations. The summaries will be given by planned time point.

- The sampling time of pre-dose samples relative to start of the dose infusion will be treated as zero;
- Concentration values below BLQ in pre-dose samples and in samples taken before the time of the first quantifiable concentration will be treated as zero;
- Post-dose BLQ concentrations flanked by quantifiable concentrations will be set to missing;
- Post-dose BLQ concentrations after the last quantifiable point will be set to missing for summary statistics of plasma concentrations;
- The mean/median value at a time point where one or more samples have BLQ values will be reported (in tabular or graphical fashion) even if the mean/median value is BLQ of the assay;
- Zero mean or median values will be included in summary tables.

It should be noted that a high proportion of BLQ values may affect the summary statistics; if more than 50% of the values are imputed (i.e., BLQ), then the summary statistics (mean, SD, median, quartiles) will not be displayed.

Summary statistics for concentration-time data will include the percentage of BLQ values relative to the total N

$$\%BLQ = 100 * (\text{number of subjects who have BLQ values} / \text{total number of subjects})$$

at each time point.

Descriptive statistics will be provided as outlined in Section 7, and in addition the CV% and geometric mean.

Individual CSL312 plasma concentration plots (on log-linear scale) will be plotted versus actual sampling time. Multiple subject plots will be presented on 1 page.

Plots for mean ( $\pm$  SD) CSL312 plasma concentrations (on linear and on log-linear scales) versus nominal (planned) time will be provided. If more than 50% of the individual values are BLQ, the mean and SD will be set to missing in the plots.

Plasma concentrations excluded from the derivation of the PK parameters will also be excluded from the summary statistics and the mean plots. A footnote will indicate if plasma concentrations have been excluded from the analysis.

A by-subject listing of CSL312 plasma concentrations with the concentrations flagged that have been excluded from the derivation of the PK parameters based on the PK Analysis Set will support the summaries.

## 12.2 Deriving and Summarizing Pharmacokinetic Parameters

For subjects belonging to the PK Analysis Set, the PK parameters provided in [Appendix 15.1](#) will be determined from the CSL312 plasma concentration-time data.

The PK parameter derivation including imputation of the values BLQ and missing data will be conducted in accordance to [PK-GDL-01](#) which gives guidance on how to derive PK parameters in the presence of missing data.

PK parameters of CSL312 will be summarized with the following statistics being provided.

Variable	Statistical Parameters:
$C_{\max}$ , $AUC_{0-\text{last}}$ , $T_{1/2}$	n, arithmetic mean, SD, CV%, minimum, median, maximum, geometric mean and geometric CV%
$T_{\max}$	n, minimum, median, and maximum

The geometric CV% will be calculated as  $100 * \sqrt{\exp(\ln(SD^2)) - 1}$ .

A by-subject listing of CSL312 PK parameters based on the PK Analysis Set will be provided.

13 CCI [Redacted]

CCI [Redacted]

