3	CSL312 PK in plasma: 
 
• Maximum plasma concentration (<math>C_{max}</math>)
 
• Time to maximum plasma concentration (<math>T_{max}</math>)
 
• Area under the plasma concentration-time curve from time zero to the time of the last measurable concentration (<math>AUC_{0-last}</math>)
 
• Terminal half-life (<math>T_{1/2}</math>)
 
	
 
• Mean (<math>\pm</math> standard deviation [SD]) and geometric mean (geometric coefficient of variation percentage [CV%]) for all PK parameters except <math>T_{max}</math>.
 
• Median (minimum, maximum) for <math>T_{max}</math>
 

CCI

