### 6.5 Pharmacokinetic Analysis Set

The PK Analysis Set comprises all subjects in the Safety Analysis Set who received any amount of CSL312 + SOC and have  $\geq 1$  blood sample available after administration of CSL312 for CSL312 concentration measurement. PK analyses will not be performed for subjects who are treated with placebo + SOC.

Technical Note: Subjects included in the Safety Analysis Set who received CSL312 and who have at least 1 blood sample for CSL312 concentration measurement after administration of CSL312 available will be included.

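### The geometric CV% formula in SAP 12.2 takes the log of the variance instead of the variance of the logs, so it gives wrong or undefined values for Cmax, AUC0-last and T1/2

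*SAP*

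**What the plan says.** SAP Section 12.2 lists the statistics for Cmax, AUC0-last and T1/2 as "n, arithmetic mean, SD, CV%, minimum, median, maximum, geometric mean and geometric CV"%. Below that table it continues: "The geometric CV% will be calculated as" followed by the expression "100 * \sqrt{\exp(\ln(SD^2)) - 1", with the closing bracket of the root after the 1. In ordinary notation this is 100 × sqrt(exp(ln(SD²)) − 1).

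The geometric CV% is a named summary measure. SAP Table 1 and Protocol Section 2.2.2 both ask, for the secondary PK endpoints, for the "geometric mean (geometric coefficient of variation percentage [CV%]) for all PK parameters except" Tmax. Protocol Section 11.6 does not include it in its list of PK statistics. SD is defined only as the standard deviation, and the visible text does not say that it is taken on log-transformed values.

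SAP Section 12 says of the PK outputs that the party responsible "will produce the TFLs for the CSL312 plasma concentrations and the PK parameters as specified below". SAP Section 6.5 limits the analysis to the active arm: "PK analyses will not be performed for subjects who are treated with placebo + SOC".

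**The concern.** For log-normal data the geometric CV is a function of the variance of the log values: 100 × sqrt(exp(s²) − 1), where s is the standard deviation of the ln-transformed data. The SAP line has the same outline, but ln is applied to the variance and so cancels against exp.

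If the line is programmed as written, the geometric CV% cells for three PK parameters will be wrong or empty. The geometric mean would then be reported with no usable measure of spread beside it, although both documents ask for the pair. If the programmer silently uses the correct formula, the output departs from the written plan, and someone validating against the SAP would not reproduce it.

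**Working it through.** **Inputs.** The formula, the parameters and the meaning of SD come from SAP Section 12.2 and SAP Table 1. The documents give no PK values, and SAP Appendix 15.1 gives only generic units (mass, volume, time). There is no stated geometric CV% to reproduce. Every geometric mean and log-scale SD below is an assumption made for illustration.

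**Step 1: simplify.** exp(ln(SD²)) = SD², so the printed expression is 100 × sqrt(SD² − 1).

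**Step 2: read SD as the original-scale SD.** This is the natural reading, because SD stands next to the arithmetic mean and CV% in the same list. The result then depends on SD alone:

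- SD = 1.02: sqrt(1.0404 − 1) gives about 20%.
- SD = 1.118: sqrt(1.25 − 1) gives 50%.
- SD = 1.414: sqrt(2 − 1) gives 100%.
- SD < 1: root of a negative number, no value.

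The mean does not enter, so these outputs are the same whatever the mean is.

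For log-normal data with geometric mean G and log-scale SD s, the original-scale SD is G × exp(s²/2) × sqrt(exp(s²) − 1).

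| Assumed G | Assumed s | Original-scale SD | Printed formula | Correct value |
|---|---|---|---|---|
| 200 | 0.2 | 41.2 | 4,121% | 20.2% |
| 200 | 0.3 | 64.2 | 6,419% | 30.7% |
| 200 | 0.5 | 120.8 | 12,078% | 53.3% |
| 0.2 (second row in a unit 1000 times larger) | 0.3 | 0.064 | undefined | 30.7% |
| 2 | 0.5 | 1.208 | 67.7% | 53.3% |

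The second and fourth rows are the same data in different units. The last row, where the radicand is 1.208² − 1 = 0.459, shows that the wrong value need not look absurd.

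**Step 3: read SD as the SD of the ln values, s.** The printed radicand is s² − 1 and the correct one is exp(s²) − 1. The difference is exp(s²) − s², which equals 1 at s = 0 and grows with s. The printed form is therefore never right.

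| s | Printed formula | Correct value |
|---|---|---|
| 0.2 | undefined (radicand −0.96) | 20.2% |
| 0.3 | undefined (−0.91) | 30.7% |
| 0.5 | undefined (−0.75) | 53.3% |
| 0.8 | undefined (−0.36) | 94.7% |
| 1.0 | 0% | 131.1% |
| 1.2 | 66.3% | 179.5% |
| 1.5 | 111.8% | 291.3% |

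On this reading no value can be computed whenever the true geometric CV is below 131.1%.

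**Step 4: try a moved bracket.** Reading the exponent as (ln SD)² does not help. With assumed G = 200 and s = 0.3 it gives about 577,000%.

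**Step 5: look for another formula.** No other visible part of either document gives one.

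**The case against.** The strongest objection is that the whole point rests on one inline formula read from a PDF by a program. A subscript, as in SD_ln², could have been flattened into ln(SD²). That cannot be excluded, and the source page should be checked before the SAP is called wrong. Against it, the %BLQ formula in SAP 12.1 and the half-life formula in Appendix 15.1 came through coherently. Even with a lost subscript, no visible text defines a log-scale SD.

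Second, SAP Section 12 places all noncompartmental analyses under the sponsor's guideline PK-GDL-01, which is not available here and might cover summary statistics. However, Section 12.2 invokes it for deriving parameters and for handling BLQ and missing values, then states the CV formula separately. Section 12 has the tables follow the SAP. The guideline therefore does not displace the printed line.

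Third, SAP Section 3 refers to a separate document with table shells and implementation details, and an experienced programmer may well use the standard formula. Many wrong outputs would also be noticed, being either missing or thousands of percent beside an ordinary CV%. This stands: it lowers the chance that wrong values would reach a report. It does not make the formula correct, and the G = 2 example shows that visibility is not assured. How likely such a case is cannot be judged, because the documents give no PK values.

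**Conclusion.** The concern holds. As extracted, the SAP 12.2 formula is not a geometric CV under any of the readings tried, and it gives a wrong or undefined value for a summary measure named for the secondary PK endpoints. That follows from algebra and needs no assumed PK values; only the worked sizes for particular geometric means do.

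It is a minor point. It affects one descriptive statistic for three parameters in one arm. Arithmetic mean, SD, CV%, geometric mean, median, minimum and maximum are unaffected, as are all efficacy and safety analyses. The correct figure can be recomputed from the by-subject PK parameter listing planned in SAP 12.2.

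Confidence is high that the formula as extracted is wrong. It is moderate that wrong values would be reported, because the implementation document cannot be seen.

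**What to change.** Check the formula on the source page of SAP 12.2. If it is printed as extracted, replace it with:

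geometric CV% = 100 × sqrt(exp(SD_ln²) − 1), where SD_ln is the standard deviation of the natural-log-transformed values of the PK parameter.

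If the page does show a log-scale subscript, add the definition of SD_ln, since none is visible. With this form the result does not depend on the unit. The cost is one line in the SAP, plus a check that the table program and the implementation document use the same expression.

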13.1 CCI [Redacted]

CCI [Redacted]

CCI

## 15 Appendices

### 15.1 PK Parameters

Term	Definition [unit]	Calculation method
AUC 0-last	Partial AUC from time point 0 to time point of the last measurable concentration [mass * time * volume  ].	AUC from the time of dosing to a specified timepoint (t), using the linear up/log down trapezoidal rule.
C max	The maximum (peak) observed plasma drug concentration [mass * volume  ]	
T 1/2	The terminal half-life [time]	$t_{1/2} = \ln(2) / \lambda_z$
T max	The time to reach maximum (peak) drug concentration in measured biological fluid [time]	

### 15.3 National Institute of Allergy and Infectious Diseases (NIAID) 8-point Ordinal Scale

The ordinal scale is an assessment of the clinical status at the first assessment of a given study day.

NIAID Score	Description
1	Death
2	Hospitalized, on invasive mechanical ventilation or ECMO
3	Hospitalized, on NIV or high-flow oxygen devices
4	Hospitalized, requiring supplemental oxygen
5	Hospitalized, not requiring supplemental oxygen – requiring ongoing medical care (COVID-19 related or otherwise)
6	Hospitalized, not requiring supplemental oxygen – no longer requires ongoing medical care
7	Not hospitalized, limitation on activities and/or requiring home oxygen
8	Not hospitalized, no limitations on activities

COVID-19 = Coronavirus Disease 2019; ECMO = extracorporeal membrane oxygenation; NIAID = National Institute of Allergy and Infectious Diseases; NIV = non-invasive ventilation.

Source: [NIAID, 2020](#).

**15.4 Glasgow Coma Scale**

Feature	Scale Responses	Score
Eye opening (E)	Spontaneous	4
	To speech	3
	To pain	2
	None	1
Best verbal response (V)	Oriented	5
	Sounds	4
	Words	3
	Confused	2
	None	1
Best motor response (M)	Obedying commands	6
	Localizing	5
	Normal flexion (withdrawal)	4
	Abnormal flexion	3
	Extension	2
	None	1
Total comma score		3-15

Source: [Teasdale et al, 2014](#).

